5. SELECTION AND WITHDRAWAL OF PATIENTS

Prospective waivers (exceptions) from study inclusion and exclusion criteria to allow patients to be randomized/enrolled are not granted by Teva ([Appendix B](#)).

5.1. Patient Inclusion Criteria

Patients may be randomized/enrolled in this study only if they meet all of the following criteria:

- a. Adults of male and female sex (without restrictions on gender) between 18 and 75 years of age, inclusive, at the time of informed consent.
- b. Diagnosis of UC or CD for ≥ 3 months.
- c. UC patients only: Patient with moderate to severe active UC as defined by the 3-component modified Mayo score of 5 to 9, inclusive, with an endoscopic subscore of ≥ 2 (from central reading).
- d. CD patients only: Patient with moderate to severe active CD as determined by a CDAI score of ≥ 220 and ≤ 450 .
- e. CD patients only: SES-CD score of ≥ 6 (≥ 4 for isolated ileal disease).
- f. UC patients only: Active disease beyond the rectum (>15 cm of active disease at the screening endoscopy [sigmoidoscopy]).
- g. Patient must have inadequate response to, loss of response to, or intolerance to:
 - At least 1 of the following therapies: corticosteroids, immunosuppressants, or an approved advanced therapy for IBD including biologics (anti-TNF, anti-integrins, anti-IL-12/23, or anti-IL-23), JAK inhibitors, or S1P receptor modulators. No more than 3 locally approved classes of biologics.
 - Inadequate response to, loss of response to, or intolerance to corticosteroid treatment is defined as 1 or more of the following:
 - Steroid refractory: persistent symptoms of active disease despite treatment with at least one 4-week induction regimen that included a dose of ≥ 30 mg prednisone (oral) daily for at least 2 weeks or intravenous (iv) for at least 1 week within the previous 5 years;
 - Steroid dependent: 2 failed attempts to taper steroids below a dose equivalent to 10 mg prednisone (oral) daily within the previous year;
 - Steroid intolerant: history of intolerance to corticosteroids (including, but not limited to, Cushing's syndrome, osteopenia/osteoporosis, hyperglycemia, insomnia, and infection) within the previous 5 years.
 - Inadequate response to, loss of response to, or intolerance to prior immunosuppressant treatment is defined by 1 or more of the following:

- Persistent signs and symptoms of active disease despite a history of at least 1 regimen of oral AZA or 6-MP and/or methotrexate consistent with the regional standard of care;
 - History of intolerance to AZA, 6-MP, or methotrexate (including, but not limited to, nausea/vomiting, abdominal pain, pancreatitis, liver function testing abnormalities, lymphopenia, thiopurine methyltransferase genetic mutation, and infection).
- Inadequate response to, loss of response to, or intolerance to prior advanced therapy for IBD (biologics, JAK inhibitors, and S1P receptor modulators) defined as 1 or more of the following:
 - Loss of response: Persistent signs and symptoms of active disease despite at least one induction and one maintenance regimen of the locally approved regimen of anti-TNF, anti-integrins, anti-IL-12/23 or anti-IL-23 mAbs, JAK inhibitors, or S1P receptor modulators.
 - Inadequate response (primary non-response): Persistent signs and symptoms of active disease despite at least one induction regimen of the locally approved highest dosing regimen of anti-TNF, anti-integrins, anti-IL-12/23 or anti-IL-23 mAbs, JAK inhibitors, or S1P receptor modulators.
 - Intolerance: Discontinuation of anti-TNF, anti-integrins, anti-IL-12/23 or anti-IL-23 mAbs, JAK inhibitors, or S1P receptor modulators due to an adverse drug reaction as determined by treating physician. Such adverse drug reactions include, but are not limited to, nausea/vomiting, abdominal pain, pancreatitis, liver function testing abnormalities, lymphopenia, and infections.
- h. If patient is taking the following agents, patient must have been on a stable dose for the following specified period of time: oral 5-ASA or sulfasalazine stable dose for at least 4 weeks prior to endoscopy, oral corticosteroids stable dose for at least 2 weeks prior to endoscopy, and 6-MP, AZA, or methotrexate stable dose for 4 weeks prior to endoscopy.
- i. The patient is able to communicate satisfactorily with the investigator and to participate in, and comply with, the requirements of the study.
- j. The patient is able to understand the nature of the study and any potential hazards associated with participating in the study.
- k. The patient must be willing and able to comply with study restrictions and to remain at the investigational center for the required duration during the study period, and willing to return to the investigational center for further visits, as applicable, and the follow-up procedures and assessments as specified in this protocol.
- l. Women of non-childbearing potential who are either surgically (documented hysterectomy, bilateral oophorectomy, or bilateral salpingectomy) or congenitally sterile as assessed by a physician, or 1-year postmenopausal (no menses for at least 12 months without an alternative medical cause plus a concentration of follicle-stimulating hormone [FSH] within the postmenopausal range [an increased concentration of FSH of more than 35 IU/L] in women not using hormonal contraception or hormonal replacement therapy).

Women of childbearing potential (WOCBP) must have a negative β -human chorionic gonadotropin (HCG) test result and practice a highly effective method of birth control (methods that can achieve a failure rate of less than 1% per year when used consistently and correctly; [Appendix D](#)) prior to IMP administration and throughout the study or 50 days after the last IMP dose, whichever is longer.

- m. Male patients (including vasectomized) with WOCBP partners (whether pregnant or not) must use condoms after the first IMP administration and throughout the study or until 50 days after the last IMP dose, whichever is longer.

5.2. Patient Exclusion Criteria

Patients will not be randomized/enrolled in this study if they meet any of the following criteria:

- a. The patient has any concomitant conditions or treatments that could interfere with study conduct, influence the interpretation of study observations/results, or put the patient at increased risk during the study as judged by the investigator and/or the clinical study physician.
- b. Diagnosis of indeterminate colitis, ischemic colitis, radiation colitis, diverticular disease associated with colitis, or microscopic colitis.
- c. Patient has colonic dysplasia or neoplasia (with exception of dysplasia on a completely excised adenomatous polyp [not a sessile one]), toxic megacolon, primary sclerosing cholangitis, known non-passable colonic stricture, presence of colonic or small bowel stoma, presence of non-passable colonic or small bowel obstruction or resection preventing the endoscopy procedure, or fulminant colitis.
- d. Presence of active enteric infections (positive stool culture) or a history of serious infection (requiring parenteral antibiotic and/or hospitalization) within 4 weeks prior to the first screening visit.
- e. Patient anticipates requiring major surgery during this study.
- f. Hepatitis B core antibody (HBcAb) or surface antigen (HBsAg) positive. If HBcAb is positive and HBsAg negative, Hepatitis B viral deoxyribonucleic acid (DNA) will be done as reflective test, and, if undetectable, then not exclusionary. Hepatitis C antibody positive with detectable ribonucleic acids (RNAs). Positive human immunodeficiency virus types 1 or 2 at screening.
- g. Tested positive for TB at screening by the QuantiFERON[®] TB Gold Test (unless documentation of prior TB treatment is available) or had a history of untreated latent or active TB.
- h. A history of an opportunistic infection (eg, cytomegalovirus retinitis, Pneumocystis carinii, or aspergillosis).
- i. A history of more than 2 herpes zoster episodes in the last 5 years or multimetameric herpes zoster.
- j. A history of or ongoing chronic or recurrent serious infectious disease (eg, infected indwelling prosthesis or osteomyelitis).

- k. Current or history of chronic liver or biliary disease (with the exception of Gilbert's syndrome, asymptomatic gallstones or uncomplicated fatty liver disease) at screening or baseline ALT or AST $>2\times$ ULN or bilirubin $>1.5\times$ ULN (isolated bilirubin $>1.5\times$ ULN is acceptable if bilirubin is fractionated and direct bilirubin $<35\%$) at screening.
- l. Absolute neutrophil count $<1.5\times 10^9/L$ or Hemoglobin $<9\text{ g/dL}$ or lymphocyte count $<0.8\times 10^9/L$ or platelet count $<100,000/\text{mL}$
- m. The patient has QTc $>480\text{ ms}$
- n. Any acute infection which in the opinion of the investigator compromises the safety of the patient.
- o. The patient is currently pregnant or lactating or is planning to become pregnant or to lactate during the study or for at least 50 days after administration of the last dose of IMP in case of early termination. Any woman becoming pregnant during the study will be withdrawn from the study.
- p. The patient has a known hypersensitivity to the IMP and/or excipients.
- q. Presence of a transplanted organ.
- r. A history of malignancy within the last 5 years (exception: basal cell carcinoma or in situ carcinoma of the cervix if successful curative therapy occurred at least 12 months prior to screening or curatively resected papillary thyroid cancer).
- s. Patient is receiving any of the following therapies within the designated time period:
 - The patient is currently using any systemic immunosuppressant or immunomodulatory biologic or nonbiologic (other than those listed in inclusion criterion "h" and those that are used for IBD) within 30 days or 5 half-lives (whichever is longer) prior to the endoscopy.
 - $>9\text{ mg/day}$ of oral budesonide or $>20\text{ mg/day}$ prednisone or equivalent within 2 weeks prior to the endoscopy.
 - Topical (rectal) treatment of 5-ASA or intravenous, intramuscular (parenteral), or enema/suppository administration of corticosteroids within 2 weeks prior to the endoscopy.
 - Biologics including anti-TNF, anti-integrins, anti-IL-12/23, or anti-IL-23 within 3 half-lives prior to randomization.
 - Small molecules including JAK inhibitors, or S1P receptor modulators, within 5 half-lives or shorter washout duration if undetectable drug levels can be demonstrated prior to randomization.
 - Other investigational procedures or products, within 30 days or 5 half-lives of investigational product prior to the endoscopy, whichever is longer.
 - Live vaccine within 14 days prior to the first screening visit. Inactivated vaccines (including approved inactivated COVID-19 vaccines) should preferably be completed 14 days before first IMP dosing. If administered during the study, it is recommended

to be at least 3 days before and after IMP administration, or as required by local country regulations.

- t. Current or history (within 2 years) of serious psychiatric disease or alcohol or drug abuse.
- u. Patients with incurable diseases, persons in nursing homes, and patients incapable of giving written informed consent.

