1.3. Schedule of Activities

Study procedures and assessments with their time points are presented in [Table 1](#). Detailed descriptions of each method of procedures and assessments are provided in Section [7](#) (efficacy assessments), Section [8](#) (safety assessments), and Section [9](#) (pharmacokinetic and other assessments). Study procedures and assessments by visit are listed in [Appendix A](#).

Exclusionary laboratory values can be retested once during the screening period. If the retested laboratory value(s) remain(s) exclusionary, the subject will be considered a screen failure. Redrawing samples if previous samples were unable to be analyzed would not count as a retest since previous result was never obtained.

Table 1: Study Procedures and Assessments

Study period	Screening (-42 to -1)	Induction period								Follow-up ^{a,b}	Early termination ^b	
		Treatment period ^a										
Study visit	Screening	1	2	3	4	5	6	7	8	9		
Study week	Week -6 to -1	Week 0	Week 2	Week 4	Week 6	Week 8	Week 10	Week 12	Week 14	Week 18		
Study day	Day -42 to -1	Day 1	Day 15	Day 29	Day 43	Day 57	Day 71	Day 85	Day 99	Day 127		
Visit window	N/A	N/A	±3 days based on previous visit									
Enrollment procedures												
Informed consent ^c	X											
Inclusion/exclusion criteria	X	X										
Demographics and medical history	X											
Vital signs												
Vital signs measurements ^d	X	X	X	X	X	X	X	X	X	X	X	
Weight (lb or kg)	X	X		X		X		X	X	X	X	
Height (in or cm)	X											
Medical procedures												
Full physical exam	X								X	X	X	
Brief physical exam				X		X		X				
ECG (12-lead) ^e	X			X		X			X		X	
Endoscopy												
Endoscopy ^f	X ^g								X		X	
Disease activity analysis												
Modified Mayo score (UC only)	X								X		X	

Study period	Screening (-42 to -1)	Induction period								Follow-up ^{a,b}	Early termination ^b
		Treatment period ^a									
Study visit	Screening	1	2	3	4	5	6	7	8	9	
Study week	Week -6 to -1	Week 0	Week 2	Week 4	Week 6	Week 8	Week 10	Week 12	Week 14	Week 18	
Study day	Day -42 to -1	Day 1	Day 15	Day 29	Day 43	Day 57	Day 71	Day 85	Day 99	Day 127	
Visit window	N/A	N/A	±3 days based on previous visit								
Stool frequency and Rectal bleeding Mayo sub-scores (PRO2 UC) ^h	X		X	X	X	X	X	X	X		X
Robarts Histopathology Index (UC only)	X								X		X
CDAI score (CD only)	X			X		X		X	X		X
Stool frequency and Abdominal pain (PRO2 CD) ^h	X		X	X	X	X	X	X			X
SES-CD (CD only)	X								X		X
MM-SES-CD (CD only)	X								X		X

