4.4. Stopping Rules for the Study

4.4.1. Individual Stopping Criteria

4.4.1.1. Permanent Individual Withdrawn from IMP

IMP will be discontinued in the event of any of the following:

- The patient develops a serious or severe infection that is:
 - Life threatening

- Requires intensive care unit admission
 - Systemic opportunistic infection including tuberculosis (including pulmonary), cytomegalovirus (CMV; including CMV colitis), and listeriosis
- The patient experiences a serious or severe hypersensitivity reaction following investigational medicinal product (IMP) administration, meeting the Common Terminology Criteria for Adverse Events (CTCAE) criteria 3 to 4:
 - Anaphylaxis
 - Allergic reaction
 - Serum sickness
- The patient experiences a serious or severe Cytokine Release Syndrome following IMP administration, defined as CTCAE grade 3 to 4.
- The patient is diagnosed with malignant neoplasm other than appropriately treated basal cell carcinoma or squamous cell carcinoma of the skin or in situ carcinoma of uterine cervix.
- The patient experiences a serious adverse event where in the investigator, after consultation with the study sponsor's medical expert, assesses there is a reasonable possibility that the serious adverse event may be caused by the IMP.
- The patient becomes pregnant (see Section 8.3).
- The patient requires prohibited medications or an increase from baseline of the medications for the treatment of UC and CD, including surgery for UC and CD (see Section 6.6.3 and Section 6.6.4).
- Neutrophil count of:
 - Absolute neutrophil count $<0.5 \times 10^9/L$ confirmed on repeat testing within 3 to 5 days
 - Absolute neutrophil count $<1.0 \times 10^9/L$ that lasts for 2 weeks (retested every 3 to 5 days) or accompanied by fever $\geq 38.5^\circ\text{C}$
- Lymphocyte count:
 - Lymphocyte count $<0.2 \times 10^9/L$ confirmed on repeat testing within 3 to 5 days
 - Lymphocyte count 0.2 to $0.5 \times 10^9/L$ that lasts for 2 weeks (retested every 3 to 5 days)
- Hemoglobin $<8 \text{ g/dL}$ or an absolute decrease of $\geq 3 \text{ g/dL}$ from baseline (confirmed in repeated test)
- Platelets $<50 \times 10^9/L$ (confirmed in repeated test)
- Liver Chemistry Stopping and Increased monitoring criteria
 - (Refer to Liver Safety Required Actions and Follow up Assessments section in [Appendix K](#))

- alanine aminotransferase (ALT) or aspartate aminotransferase (AST) $\geq 5x$ upper limit of normal (ULN)

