- ALT or AST $\geq 3x$ ULN with the appearance of fatigue, nausea, vomiting, right upper quadrant pain or tenderness, fever, rash, and/or eosinophilia ($>5\%$)
- AST and/or ALT ≥ 3 fold ULN combined with an elevation of total bilirubin ≥ 2 fold ULN measured in the same blood draw sample or in combination with clinical jaundice or in combination of International Normalized Ratio (INR) >1.5 (not applicable for patients on anticoagulants)
- ALT $\geq 3x$ ULN for 4 weeks
- ALT $\geq 3x$ ULN and cannot be monitored weekly for 4 weeks
- QTc >500 msec or change from baseline of QTc >60 msec

4.4.1.2.Temporary Withholding of IMP

IMP will be temporarily discontinued in the event of any of the following:

- Mild or moderate infusion reactions (grade 1 to 2 according to CTCAE of “allergic reaction”) during the infusion. The infusion may be re-initiated, at the discretion of the investigator, at lower speed with or without appropriate premedication, if symptoms are resolved within 1 hour after the stop of infusion/injection. If symptoms return, IMP should be discontinued immediately and permanently.
- A clinically significant infection that the investigator believes may be related to, or exacerbated by, ongoing treatment with the IMP, and none of the permanent stopping rules have been met.
- Absolute neutrophil count $<1.0 \times 10^9/L$
 - Re-testing should be undertaken within 3 to 5 days, and should be re-tested every 3 to 5 days until values have returned to $>1.5 \times 10^9/L$, at which point dosing can be resumed. If the scheduled dose window is missed, re-initiation of study treatment intervention should be restarted as soon as possible but should not result in two consecutive doses being given less than 7 days apart.
- ALT $>3x$ ULN and $<5x$ ULN and bilirubin $<2x$ ULN, without symptoms believed to be related to liver injury or hypersensitivity, and who can be monitored weekly for 4 weeks may continue IMP after discussion with sponsor’s medical expert. If, after 4 weeks of monitoring, ALT $<3x$ ULN and bilirubin $<2x$ ULN, patient will be monitored twice monthly until liver chemistries normalize or return to within baseline. (Refer to Liver Safety Required Actions and Follow up Assessments section in [Appendix K](#)).

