If any of the following criteria occur, study drug should be withheld and additional monitoring and follow-up assessment will be required (as detailed in the Liver Safety Required Actions and Follow-up Assessments section in [Appendix K](#)):

- ALT or AST ≥ 5 x ULN
- ALT or AST ≥ 3 x ULN with the appearance of fatigue, nausea, vomiting, right upper quadrant pain or tenderness, fever, rash, and/or eosinophilia ($>5\%$)
- AST and/or ALT ≥ 3 fold ULN combined with an elevation of total bilirubin ≥ 2 fold ULN measured in the same blood draw sample or in combination with clinical jaundice or INR >1.5 (not applicable for patients on anticoagulants)

The additional information will be recorded on the Liver Event CRF.

The most appropriate diagnosis or the abnormal laboratory values (if a diagnosis cannot be established) should be recorded on the Adverse Event eCRF (see Section [8.1.3](#)) and reported to the Sponsor immediately (ie, no more than 24 hours after learning of the event).

Severe hematology abnormalities

Predefined confirmed hematology stopping criteria (see Section [4.4.1](#)) should be re-tested every 3 to 5 days until values have returned to above the hematological exclusion criteria threshold, at which point dosing can be resumed (however, two consecutive doses of IMP, should never be given less than 7 days apart).

8.1.10.2. Protocol-Defined Adverse Events of Special Interest that Do Not Require Reporting to Sponsor's Global Patient Safety and Pharmacovigilance

The following are considered protocol-defined adverse events of special interest that do not need to be sent to the sponsor's GPSP department (unless assessed as serious) and will be recorded only in the clinical database:

- administration site reactions (as described in Section [8.2](#))

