8.5.1. Serum Chemistry, Hematology, and Urinalysis

Clinical laboratory tests (serum chemistry, hematology and coagulation, urinalysis) will be performed at the time points detailed in [Table 1](#). Patients should be fasting for at least 8 hours prior to safety laboratory assessments only at the screening, week 14, and early termination visits. Clinical laboratory tests will be performed using the central laboratory. Local laboratory testing can be used under extenuating circumstances and only following agreement with the sponsor.

Screening laboratory test abnormalities, if considered by the Investigator to be transient and inconsistent with the patient's clinical condition, may be repeated once during the screening period for confirmation. Redrawing samples if previous samples were unable to be analyzed would not count as a retest since previous result was never obtained.

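### Exclusion criterion l states the platelet limit per mL, which is 0.1 × 10^9/L and 500-fold below the protocol's own permanent stopping limit

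*Protocol*

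**What the plan says.** Section 5.2, criterion l, sets four hematology limits for entry. Neutrophils and lymphocytes are given in units of 10^9/L and hemoglobin in g/dL. Platelets are given as "platelet count $<100,000/\text{mL". No other current section restates the platelet entry limit.

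Section 4.4.1.1, on permanent withdrawal from study drug, sets the platelet criterion as "Platelets $<50 \times 10^9/L$ (confirmed in repeated test". It also gives fixed stopping limits for neutrophils, lymphocytes and hemoglobin.

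The entry limits are used in two further places:

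- Section 1.3 allows one retest of an exclusionary laboratory value and then states: "If the retested laboratory value(s) remain(s) exclusionary, the subject will be considered a screen failure".
- Section 8.1.10.1, on severe hematology abnormalities, refers to the stopping criteria of Section 4.4.1 and requires retesting "until values have returned to above the hematological exclusion criteria threshold, at which point dosing can be resumed".

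**The concern.** An entry limit for a blood count should be stricter than the level at which treatment is stopped. Otherwise a patient can qualify for randomisation and meet the stopping rule on the same result. Criterion l follows that order for three of its four parameters and reverses it for platelets.

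What is at stake is eligibility and safety, not inference. Section 5 grants no prospective waivers from the criteria, so their wording has to be exact. The limit also serves, by reference, as a resumption level in Section 8.1.10.1, so a wrong unit carries over to any reader who applies that section.

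**Working it through.** **Inputs.** Entry limits come from Section 5.2, criterion l. Stopping limits come from Section 4.4.1.1. The protocol reports no calculation behind the platelet figure, so there is nothing to reproduce; the check is a unit conversion and a comparison.

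**Conversion as printed.** 100,000 per mL × 1,000 mL per L = 1 × 10^8 per L = 0.1 × 10^9/L.

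**Stopping limit over entry limit.** 50 / 0.1 = 500.

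**Comparison with the other three parameters.** Each entry limit is divided by the highest fixed stopping limit for that parameter.

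| Parameter | Entry limit | Fixed stopping limits | Entry / highest stop |
|---|---|---|---|
| Neutrophils (10^9/L) | 1.5 | 0.5 confirmed; 1.0 if sustained for 2 weeks or with fever | 1.5 / 1.0 = 1.5 |
| Lymphocytes (10^9/L) | 0.8 | 0.2 confirmed; 0.2 to 0.5 if sustained for 2 weeks | 0.8 / 0.5 = 1.6 |
| Hemoglobin (g/dL) | 9 | 8 | 9 / 8 = 1.125 |
| Platelets as printed (10^9/L) | 0.1 | 50 | 0.1 / 50 = 0.002 |
| Platelets if per microlitre (10^9/L) | 100 | 50 | 100 / 50 = 2.0 |

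The last row uses 100,000 per microlitre × 10^6 microlitres per L = 100 × 10^9/L. With that unit, platelets fall into line with the other three. This is the internal evidence for the intended value; the protocol does not state it.

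**Consequence at entry.** A platelet count of 30 × 10^9/L exceeds 0.1 × 10^9/L, so criterion l does not exclude it. It is below 50 × 10^9/L, so if confirmed it meets the permanent stopping rule.

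**The separate conflict on resumption.** Section 4.4.1.1 lists its hematology criteria as permanent stops. Section 8.1.10.1 says that dosing can resume after confirmed hematology stopping criteria are met, once values are back above the entry limits. A temporary rule that would reconcile the two exists only for neutrophils: Section 4.4.1.2 withholds drug below 1.0 × 10^9/L "until values have returned to $>1.5 \times 10^9/L$, at which point dosing can be resumed", which equals the neutrophil entry limit. Lymphocytes, hemoglobin and platelets have no temporary rule in Section 4.4.1.2. The conflict is therefore not created by the platelet unit and would remain after the unit is corrected.

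**The case against.** The strongest reply is that this is a one-character slip with little practical effect. Most of that stands:

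- Sites are likely to read the limit per microlitre.
- Criterion a excludes anyone whose conditions could "put the patient at increased risk during the study as judged by the investigator and/or the clinical study physician".
- Section 8.5.1 provides that "Clinical laboratory tests will be performed using the central laboratory".
- Table 1 schedules laboratory tests at weeks 0, 4, 8, 12 and 14, so the correctly stated stopping rule would act on a wrongly enrolled patient, although it would not prevent entry.
- Section 8.1.10.1 makes severe hematology abnormalities events of special interest, reported by the serious adverse event process.
- The protocol shows no affected patient.

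A second reply is that the unit could be an artefact of reading the PDF. It cannot be fully excluded, and no per-microlitre unit elsewhere in the text tests how that symbol is read. It is the less likely explanation: the same unit appears in the copies of the criterion in the Amendment 01 and Amendment 03 with Revision 01 change tables, and the micro sign survives in the concentration units of Section 6.3.1.

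Two stronger readings are tempting and should not be drawn. A reader might infer that the wrong unit removes platelet protection on re-dosing, since nearly any count that triggered a stop already exceeds 0.1 × 10^9/L. But Section 4.4.1.1 permanently stops a patient with a confirmed count below 50 × 10^9/L, in the right unit. Re-dosing would follow only if Section 8.1.10.1 were allowed to override it, which is the separate conflict. A reader might also take Section 1.3 to mean that a patient fails screening only after a retest. It does not say so: retesting is optional, and Section 5.6 defines screen failure by the criteria alone.

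**Conclusion.** The platelet limit in criterion l is wrong as written: 0.1 × 10^9/L as printed, 500-fold below the permanent stopping limit, and the only one of four hematology entry limits in the wrong order. Taken literally, it excludes almost no patient on platelets. It should be corrected because it is an operative eligibility threshold. The expected practical effect is small, for the reasons above, and there is none on sample size, power or the efficacy analysis.

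The conclusion rests on the text reproducing the source unit faithfully. That 100 × 10^9/L was intended is an inference from the pattern of the other limits and needs the sponsor's confirmation. The conflict between Sections 4.4.1.1 and 8.1.10.1 is a second, independent defect covering all hematology parameters; it should not be counted as a consequence of the unit error.

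**What to change.** 1. Restate the platelet limit in criterion l as below 100 × 10^9/L (100,000 per microlitre), after checking the source document and obtaining the sponsor's confirmation of intent. This is a one-line correction by letter or amendment.
2. Check that the eligibility checks in use apply that unit. A listing of screening platelet counts for randomised patients would be an inexpensive precaution, though nothing in the protocol signals a problem.
3. Separately, add one sentence stating whether the permanent stop in Section 4.4.1.1 or the resumption rule in Section 8.1.10.1 governs after a confirmed hematology stopping criterion. If resumption is meant to be possible, the hemoglobin limb "or an absolute decrease of $\geq 3 \text{ g/dL}$ from baseline (confirmed in repeated test" needs its own resumption level: a fall from 13 to 10 g/dL meets the stopping rule (13 − 10 = 3) while 10 is still above the entry limit of 9.

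The cost is a unit correction, a clarifying sentence and a short data check. No analysis or design feature changes.
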